#### **7.6 Follow-up of subjects withdrawn from treatment**

Not applicable.

#### **7.7 Premature termination of the study**

Study participants can withdraw their consent at any time during the study. Patients that experience eye fatigue, nausea or disorientation will not be included in this study. In addition, since all the elements of this study are harmless and carry no significant risks, it is unlikely that premature termination will occur during the study.

#### **7.8 Potential risk analysis due to COVID-19 regulations**

The main risk for our study due to unexpected upscaling of COVID-19 regulations would be the delay of elective CABG surgery. This would be due to a (temporary) reduced intensive care unit capacity. However, this would not impact the study feasibility, as a consequence the study will take longer to include the target number of inclusions.

## 8. SAFETY REPORTING

### 8.1 Temporary halt for reasons of subject safety

In accordance to section 10, subsection 4, of the WMO, the investigating group will suspend the study if there is sufficient ground that continuation of the study will jeopardise subject health or safety. The investigating group will notify the accredited METC without undue delay of a temporary halt including the reason for such an action. The study will be suspended pending a further positive decision by the accredited METC. The investigator will take care that all subjects are kept informed.

### 8.2 AEs and SAEs

#### 8.2.1 Adverse events (AEs)

Adverse events are defined as any undesirable experience occurring to a subject during the study considered caused by the study. All adverse events caused by the study will be reported and recorded by the investigator or his staff.

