##### 4.3 Exclusion criteria

A potential subject who meets any of the following criteria will be excluded from participation in this study:

- Major comorbidities besides coronary artery disease
- Complicated surgical procedure
- Hearing and/or visual impairments
- Psychiatric impairments
- Complaints of vomiting and nausea
- History of epilepsy
- Claustrophobia
- Facial wounds and skin defects at site of application
- Patients placed in clinical isolation
- Readmission to the intensive care unit

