### 6.2 Summary of findings from non-clinical studies

This device is developed with evidence based efficiency of VR treatment modalities in reducing pain and anxiety throughout different medical fields. See the literature review of the Healthy Mind VR device for an extensive description of these previous studies.[9]

At the current moment there are no completed studies in which the Healthy Mind VR device is used as investigational product. However, there are several ongoing clinical trials in France and Switzerland.

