### **7.2 Randomisation, blinding and treatment allocation**

For randomisation, we use a simple random allocation approach. This randomization sequence will be prepared in SPSS 26.0 (SPSS Inc, Chicago, IL) for Windows. This randomization will be performed postoperatively by the research team, in case of an uncomplicated procedure, directly after the patient returns to the clinical ward after surgery. Blinding however, is not possible in this study as usage of the medical device is clear.

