#### 8.2.2 Serious adverse events (SAEs)

A serious adverse event is any untoward medical occurrence or effect caused by the study that

- results in death;
- is life threatening (at the time of the event);
- requires hospitalisation or prolongation of existing inpatients' hospitalisation;
- results in persistent or significant disability or incapacity;
- is a congenital anomaly or birth defect; or
- any other important medical event that did not result in any of the outcomes listed above due to medical or surgical intervention but could have been based upon appropriate judgement by the investigator.

An elective hospital admission will not be considered as a serious adverse event.

The direct investigator will report all SAEs which are caused by the study to the principal investigator without undue delay after obtaining knowledge of the events.

The investigator will report these SAEs through the web portal *ToetsingOnline* to the accredited METC that approved the protocol, within 7 days of first knowledge for

SAEs that result in death or are life threatening followed by a period of maximum of 8 days to complete the initial preliminary report. All other SAEs will be reported within a period of maximum 15 days after the investigator has first knowledge of the serious adverse events.

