### **8.3 Follow-up of adverse events**

All AEs will be followed until they have abated, or until a stable situation has been reached. Depending on the event, follow up may require additional tests or medical procedures as indicated, and/or referral to the general physician or a medical specialist. SAEs need to be reported till end of study within the Netherlands, as defined in the protocol

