### **11.3 Annual progress report**

The investigator will submit a summary of the progress of the trial to the accredited METC once a year. Information will be provided on the date of inclusion of the first subject, numbers of subjects included and numbers of subjects that have completed the trial, serious adverse events/ serious adverse reactions, other problems, and amendments.

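### Section 8.2.1 records an adverse event only if it is attributed to the study, so the open-label record yields no observed control rate for nausea, dizziness/disorientation or eye fatigue

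*Combined protocol and SAP*

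**What the plan says.** Section 8.2.1 defines the event: "Adverse events are defined as any undesirable experience occurring to a subject during the study considered caused by the study". Its recording rule carries the same condition: "All adverse events caused by the study will be reported and recorded by the investigator or his staff". Causation is thus required both for an experience to count as an AE and for it to be written down. The section says who records events, not who judges causation.

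The trial is unblinded (section 7.2): "Blinding however, is not possible in this study as usage of the medical device is clear". Controls receive conventional care without the device (section 3). The named device risks are nausea and dizziness (Summary), and eye fatigue, disorientation and nausea (sections 6.3 and 10.3). On prior experience, section 6.2 says: "At the current moment there are no completed studies in which the Healthy Mind VR device is used as investigational product".

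Section 7.3 measures NRS, QoR-15, STAI-6 and analgesic use in both arms, twice a day on days 1 to 3, and names no symptom item. Sections 7.1 and 9.1 contain no safety parameter and no AE analysis. Section 8.3 adds a follow-up duty: "All AEs will be followed until they have abated, or until a stable situation has been reached".

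**The concern.** Nausea, dizziness and tired eyes can occur after cardiac surgery with or without a headset. Under 8.2.1 such a symptom in a control patient enters the record only if someone considers it caused by the study, which is unlikely in an arm without a device. In the VR arm the same symptom is recorded or not according to a judgement that is presumably made with knowledge of the arm.

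A VR-arm count could then be background symptoms credited to the headset, or an undercount because headset symptoms were put down to surgery. The record cannot separate the two. What is at stake is the usefulness of the only safety information this trial would generate on the device, not any efficacy result.

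**Working it through.** The documents give no AE rate, so there is no figure of the plan's own to reproduce. The only design figure, the NRS power in section 4.4, does not bear on this point.

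**Step 1: is the control rate available elsewhere?** Section 7.3 lists four outcomes for both arms, none of them a symptom item. QoR-15 is collected in both arms, but the protocol does not list its items and section 9.1 plans it only as a score. It cannot be credited with supplying a symptom rate. No section explicitly calls for these symptoms to be recorded regardless of cause.

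**Step 2: what would the VR-arm count be with no device effect?** Inputs: n = 50 per arm (section 4.4); background rate b and the share of background symptoms attributed to the study a_b are assumptions. Expected recorded count = 50 × b × a_b.

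- b = 5%, a_b = 10%: 50 × 0.05 × 0.10 = 0.25
- b = 10%, a_b = 25%: 50 × 0.10 × 0.25 = 1.25
- b = 20%, a_b = 50%: 50 × 0.20 × 0.50 = 5.0
- b = 30%, a_b = 75%: 50 × 0.30 × 0.75 = 11.25

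**Step 3: what true excess fits a given count?** Let d be the true VR excess and a_d the share of device symptoms attributed to the study, treating the two sources as additive. The recorded rate is r = a_b·b + a_d·d, so d = (r − a_b·b)/a_d. For 5 of 50, r = 0.10:

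- b = 20%, a_b = 0.5, a_d = 1: (0.10 − 0.10)/1 = 0 points
- no background contribution, a_d = 1: 0.10/1 = 10 points
- no background contribution, a_d = 0.5: 0.10/0.5 = 20 points
- b = 5%, a_b = 0.5, a_d = 1: (0.10 − 0.025)/1 = 7.5 points

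At 5% background, with every device symptom attributed, moving a_b from 0 to 0.5 changes the answer only from 10 to 7.5 points. Under-attribution of device symptoms is a separate source. With a_d = 0.5 the same range becomes 0.10/0.5 = 20 to 0.075/0.5 = 15 points.

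**Step 4: what would recording in both arms give?** 95% half-width = 1.96 × √[p1(1−p1)/n1 + p2(1−p2)/n2].

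| Control rate | Equal rates, 50/50 | VR 10 points higher, 50/50 | Equal rates, 40 VR/60 control | VR 10 points higher, 40/60 |
|---|---|---|---|---|
| 10% | 11.8 | 13.9 | 12.0 | 14.5 |
| 20% | 15.7 | 16.9 | 16.0 | 17.4 |
| 30% | 18.0 | 18.6 | 18.3 | 19.1 |

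Example: at 10% in both arms, 1.96 × √(2 × 0.09/50) = 1.96 × 0.06 = 11.8 points. The 40/60 columns are included because simple randomisation of 100 (section 7.2) gives an arm size of 50 ± 1.96 × 5, roughly 40 to 60. Every entry exceeds 10 points, so a 10-point excess could not be distinguished from none.

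**The case against.** The strongest reply is that safety is neither a study parameter nor an analysis, that the device is CE class I, and that causality-limited recording after major surgery is a defensible choice. It stands to this extent: no planned result changes, and a full all-cause AE definition after CABG would add many entries and widen the follow-up duty in 8.3 for little gain.

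The background may also be low. Section 4.3 excludes "Complaints of vomiting and nausea", and section 7.7 says that patients with eye fatigue, nausea or disorientation will not be included. If both are read as entry conditions, rates near 5% are plausible. That also stands, although 7.7 can equally be read as a removal rule, and neither section measures the rate.

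The remedy is imprecise and remains unblinded self-report. True, but it supplies an observed control rate and takes the attribution step out of the count.

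A reader might infer more than the documents support:

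- *That SAEs are filtered in the same way.* In the 8.2.2 definition, the causal phrase may qualify only the word effect, and section 11.3 lists "serious adverse events/ serious adverse reactions, other problems, and amendments". Only the reporting sentence is clearly limited: "The direct investigator will report all SAEs which are caused by the study to the principal investigator without undue delay".
- *That control events cannot be recorded.* The definition is not arm-specific; a near-zero control count is an inference about attribution.
- *That the trial claims to test its benefit-risk statement.* The statements in the Summary and sections 10.3 and 12.2 are forward-looking justifications for running the study.
- *That a false safety signal is likely to be declared.* No test of AEs is planned.

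**Conclusion.** The point holds as a cheap improvement. Section 8.2.1 states a rule that makes the AE record depend on attribution in an unblinded trial whose controls have no device, and no other section explicitly fills the gap. The record therefore gives no observed control rate for the device's named symptoms.

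Its size cannot be fixed from the documents. Under the assumed rates above, 5 of 50 is compatible with a true excess anywhere from 0 to 20 points; near 5% background, the part due to background attribution shrinks to about 2.5 points (10 − 7.5). The structural point does not depend on these assumptions, but its practical weight does. That whoever assesses causation knows the arm is inferred from section 7.2, not stated in 8.2.1. The efficacy analyses are untouched.

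**What to change.** 1. In 8.2.1, add that nausea, dizziness/disorientation and eye fatigue are recorded in both arms whether or not considered related, with relatedness as a separate field. The definition for other AEs need not change, and SAE reporting can stay as written.
2. Ask these as three yes/no items at the existing day 1-3 measurement moments in both arms. The recall window runs from randomisation at the first moment and from the previous moment after that.
3. Report, per arm, the proportion with at least one yes for each symptom, and the risk difference with a 95% confidence interval, descriptively and without a test.
4. State in 8.3 whether follow-up covers every recorded event or only those considered related.
5. Reconcile sections 6.3 and 12.1(e), which end participation once symptoms are noticed, with 7.5, which deletes data on withdrawal, and 7.7, whose meaning is unclear. Symptom answers already given should be kept for everyone randomised, as far as consent allows; otherwise the added questions could themselves cost data. Whether a symptomatic participant continues VR is not addressed here.

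Cost: up to six short question sets per participant (two moments on each of three days), one extra field, more entries, and wording in 8.2.1 and 8.3. Step 5 is the larger task and has to be settled before the items are introduced. The answers remain unblinded self-report.

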#### 8.2.2 Serious adverse events (SAEs)

A serious adverse event is any untoward medical occurrence or effect caused by the study that

- results in death;
- is life threatening (at the time of the event);
- requires hospitalisation or prolongation of existing inpatients' hospitalisation;
- results in persistent or significant disability or incapacity;
- is a congenital anomaly or birth defect; or
- any other important medical event that did not result in any of the outcomes listed above due to medical or surgical intervention but could have been based upon appropriate judgement by the investigator.

An elective hospital admission will not be considered as a serious adverse event.

The direct investigator will report all SAEs which are caused by the study to the principal investigator without undue delay after obtaining knowledge of the events.

The investigator will report these SAEs through the web portal *ToetsingOnline* to the accredited METC that approved the protocol, within 7 days of first knowledge for

SAEs that result in death or are life threatening followed by a period of maximum of 8 days to complete the initial preliminary report. All other SAEs will be reported within a period of maximum 15 days after the investigator has first knowledge of the serious adverse events.

### **8.3 Follow-up of adverse events**

All AEs will be followed until they have abated, or until a stable situation has been reached. Depending on the event, follow up may require additional tests or medical procedures as indicated, and/or referral to the general physician or a medical specialist. SAEs need to be reported till end of study within the Netherlands, as defined in the protocol

## 9. STATISTICAL ANALYSIS

### 9.1 Primary study parameters

The included data (NRS score, STAI-6 score, QoR-15 score) will be presented as mean  $\pm$  standard deviation. Ratios will be given for statistical assessment of non-continuous variables (assessment of analgesic use). Because the data is expected to be non-normally distributed, Wilcoxon (Mann-Whitney) Rank-Sum testing will be performed to analyze differences between groups. Differences between groups will be assessed for each measurement at each point in the study (day 1, 2 and 3) and cumulative as mean values. SPSS 26.0 (SPSS Inc, Chicago, IL) for Windows is used to assess statistical analyses.

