## 2. OBJECTIVES

Primary Objective: To investigate the effect of VR distraction therapy with breathing exercises in post-operative pain and anxiety management in cardiac surgery patients undergoing coronary artery bypass grafting (CABG) procedure.

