##### 4.4 Sample size calculation

In total, 100 subjects will be included in this study. 50 subjects in the patient group that will receive VR therapy and 50 subjects in the patient group that will not receive VR therapy. Since literature is limited about our primary outcomes in the field of cardiac surgery, a retrospective pilot was done in our clinical pool of CABG patients for the assessment of one of our primary outcomes (NRS-score) upon which we based our sample size calculation. See below for details.

A retrospective assessment for NRS-score is performed in 35 patients who have undergone an uncomplicated CABG procedure in our department the past year (2020). Since the data was non-normally distributed, a two-sided Wilcoxon (Mann-Whitney) Rank-Sum test was performed in nQuery Advisor version 8.5.1 [8] on Windows with  $P(X < Y) = 0.5$  and a test significance level of 0.05. Since this statistical test allows only a maximum

of 8 categories and none of the pilot patients scored 0, 9 or 10 for the NRS-score, only NRS-scores 1 - 8 were used as categories in this test. This resulted in a power of 92,7% for a sample size of 100 subjects (50 per group) (**Table 1**).

MTT2-1 / Wilcoxon (Mann-Whitney) Rank-Sum Test that $P(X < Y) = 0.5$		
	1	2
Test Significance Level, $\alpha$	0,050	0,050
1 or 2 Sided Test?	2	2
Number of Categories, k	8	8
Side Table Name	MTT2S-1	MTT2S-2
$p_1 = P(X < Y)$	0,311	
Power (%)	92,7	92,7
▶ Sample Size per Group, n	50	50

  

Category	Proportion in Group 1 (X)	Proportion in Group 2 (Y)
1	0,059	0,050
▶ 2	0,059	0,302
3	0,088	0,180
4	0,328	0,250
5	0,119	0,050
6	0,147	0,090
7	0,060	0,060
8	0,140	0,018
$\sum \pi_i$	1,000	1,000
$p_1 = P(X < Y)$	0,311	

**Table 1.** Sample size calculation using a two-sided Wilcoxon (Mann-Whitney) Rank-Sum test in nQuery Advisor version 8.5.1 on Windows with  $P(X < Y) = 0.5$ .

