## **7. METHODS**

### **7.1 Study parameters**

#### **7.1.1 Main study parameters**

The main study parameters are:

- Numeric Rating Scale (NRS) to assess the effect of pain on mobility
- Quality of Recovery-15 (QoR-15) questionnaire
- State-Trait Anxiety Inventory-6 (STAI-6) questionnaire
- Assessment of analgesic use

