### **7.3 Study procedures**

The study will consist of 100 participants who have undergone an uncomplicated surgical CABG procedure.

The intervention group includes 50 patients using a VR distraction therapy device with 3D interactive nature environments in the post-operative stage for pain and anxiety management. The control group includes 50 patients who will be treated with conventional post-operative pain and anxiety management.

The intervention group will test-use the VR distraction therapy device on the day of clinical admission prior to surgery and use it therapeutic at day 1, 2 and 3 after surgery on the general ward.

Daily usage of the VR distraction therapy device consists of two sessions each day (morning and afternoon) with a duration of 20 minutes per session. The specific virtual environment for each session will be selected freely by the participants.

Outcomes will be measured daily, at the end of each session, which is done 1) after the doctor's ward visit in the morning and 2) after the shift change of the nurse team.

Outcomes will be measured at the same aforementioned moments in the control group.

Outcomes will be measured by using the Numeric Rating Scale (NRS) to assess the effect of pain on mobility, Quality of Recovery-15 questionnaire, State-Trait Anxiety Inventory-6 questionnaire and assessment of analgesic use.

At follow-up, participants will be called to gather one-time QoR-15 and STAI-6 questionnaire data 6 weeks after the surgery.

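### Four unranked primary outcomes, each compared on three days and as a mean, with no decisive test, order, adjustment or analysis significance level; the stated power covers one NRS comparison only

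*Combined protocol and SAP*

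**What the plan says.** All references are to the combined protocol and SAP.

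- **Section 2** sets a joint aim: "To investigate the effect of VR distraction therapy with breathing exercises in post-operative pain and anxiety management".
- **Section 7.1.1** opens with "The main study parameters are" and lists four items without rank: NRS, QoR-15, STAI-6 and analgesic use.
- **Section 4.4** sizes the trial on "one of our primary outcomes (NRS-score) upon which we based our sample size calculation". It uses a two-sided rank-sum test with "a test significance level of 0.05" and reports: "This resulted in a power of 92,7% for a sample size of 100 subjects (50 per group". It does not say which day, or what average over days, the NRS value represents.
- **Section 9.1**, headed as the analysis of the primary parameters, plans rank-sum comparisons between groups "for each measurement at each point in the study (day 1, 2 and 3) and cumulative as mean values". For analgesic use it says only: "Ratios will be given for statistical assessment of non-continuous variables (assessment of analgesic use". It states no significance level.
- **Section 7.3** says: "Outcomes will be measured daily, at the end of each session". There are two sessions a day, and controls are assessed at the same moments.
- **The Summary** mentions the 6-week QoR-15 and STAI-6 in its main-endpoints paragraph. Section 9.1 does not mention them.

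**The concern.** A confirmatory trial should let a reader say beforehand which result decides it. This plan does not. It has four primary outcomes, each with up to four comparisons. Nothing says which one counts, in what order they are read, or how the error rate is shared among them. As written, any of 12 to 16 results could be reported as a positive primary finding, and a reader could not tell whether it had been chosen in advance.

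The tested values are also open. Section 9.1 does not say how two session readings form a daily or cumulative value, and the 6-week data have no assigned role. Both add choices that could be made after the data are seen. Section 7.2 says blinding is impossible, and three of the four outcomes are self-reported, so advance specification is one of the main safeguards left.

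The power statement has the matching problem: it describes one test at 0.05, not the set of comparisons in section 9.1.

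**Working it through.** **1. Number of tests.** Take one value per outcome per day. Each outcome then has three daily comparisons plus one cumulative comparison, which is 4.

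- Three scores: 3 × 4 = 12.
- With analgesic use tested the same way: 4 × 4 = 16.

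Testing the two daily readings separately, or adding the 6-week data, would raise the count.

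**2. The plan's own power.** Inputs are the Table 1 proportions for NRS 1 to 8:

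- X: 0.059, 0.059, 0.088, 0.328, 0.119, 0.147, 0.060, 0.140
- Y: 0.050, 0.302, 0.180, 0.250, 0.050, 0.090, 0.060, 0.018

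p1 = P(X<Y) + ½P(X=Y) = 0.2395 + 0.0720 = 0.3115 (stated: 0.311).

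The tie-corrected Mann-Whitney test was simulated with 50 per group and 200,000 runs. Power at two-sided 0.05 is 92.7%, which equals the stated figure. The claim in section 4.4 is therefore correct for one NRS test whose values follow Table 1.

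**3. Chance of at least one false positive, each test at 0.05.** Section 9.1 gives no level, so 0.05 is borrowed from section 4.4.

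If the tests were independent, the chance is 1 − 0.95^k: 18.5% for k = 4, 46.0% for k = 12 and 56.0% for k = 16. The tests are not independent, and the documents give no correlations. Correlated normal test statistics were therefore simulated under the null (200,000 runs per setting). The assumed correlations were 0.5 to 0.9 between days and 0.3 to 0.9 between outcomes.

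| Tests | Both correlations 0.9 | Days 0.5, outcomes 0.3 |
|---|---|---|
| 16 (four outcomes) | 15% | 40% |
| 12 (three scores) | 14% | 33% |
| 4 cumulative only | 9% | 17% |

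The low ends need a correlation of 0.9 between outcomes as different as pain, anxiety, recovery and analgesic use.

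**4. NRS power if alpha is split over four outcomes.** The level is 0.05/4 = 0.0125. The simulation in step 2 gives about 81%, again with 50 per group and Table 1 distributions.

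**5. If the tested NRS value is a three-day mean.** A mean of three days need not follow Table 1. Assume Table 1 margins on each day and a day correlation of 0.5 to 0.9 (Gaussian copula, 50 per group, 20,000 runs):

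| Effect present on | Power at 0.05 | Power at 0.0125 |
|---|---|---|
| three days | 94% to 98% | 85% to 94% |
| two days | 66% to 77% | 44% to 57% |
| one day | 24% to 26% | 10% to 12% |

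These figures illustrate why the summary must be defined before a power is quoted. They do not predict the trial's result.

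**The case against.** - **NRS is primary because it sized the trial.** Section 4.4 itself calls NRS one of several primary outcomes, and section 2 aims at pain and anxiety together. Even with NRS as primary, the choice among day 1, 2, 3 or the mean stays open.
- **This is a feasibility study.** The Summary and section 1 use that word, and side-by-side reporting is tolerable in exploratory work. But section 2 states an effect objective, section 4.4 makes a formal power claim, and sections 7.1.1 and 7.1.2 contain no feasibility endpoint.
- **The plan never says that one success is enough.** That is true. If all four outcomes had to succeed, type I error would not inflate and power would fall instead. No text supports that reading, and the chance of at least one false positive at 0.05 does not depend on a success rule. What stands is that the success criterion is undefined.
- **The error rates rest on chosen correlations.** This is also true. A different set (0 to 0.7 between outcomes, 0.3 to 0.8 between days) gives 24% to 47% for 16 tests. The exact figure is uncertain, but every setting examined is well above 5%.
- **The 81% assumes 50 analysed per arm.** This stands as a caveat. Section 7.5 deletes the data of withdrawn subjects, and section 4.4 makes no dropout allowance. With 48 per arm the figure is about 79%. The stated 92.7% carries the same condition.
- **The 6-week data fall outside section 9.1.** This is a reasonable reading, since section 9.1 names only days 1 to 3. A single sentence would settle it.

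**Conclusion.** The concern holds and must be fixed, with high confidence. The plan sets no rule for which of 12 to 16 comparisons decides the trial, and no significance level for any of them. Read at 0.05 each, the chance of at least one false positive is about 14% to 40% across the two counts. This assumes one value per outcome per day and the correlations stated in the working; it exceeds 5% even in the most favourable case. The 92.7% is arithmetically right but applies to a single NRS test at two-sided 0.05, with 50 analysed per group and values distributed as in Table 1.

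**What to change.** Revise sections 7.1.1, 9.1 and 4.4 in one of two ways.

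**(a) Keep four primary outcomes**, which fits the objective in section 2. Specify one cumulative day 1 to 3 comparison per outcome, name the test for analgesic use, and apply Holm or Bonferroni across the four at two-sided 0.05.

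**(b) Name one NRS comparison as the single primary test** at two-sided 0.05. Test STAI-6, QoR-15 and analgesic use afterwards, in a fixed sequence or by Holm, and align the wording of section 2.

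Under either option:

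- Define how the two daily readings form the daily and cumulative values, for example the mean of the two and then the mean of days 1 to 3.
- Report day-by-day comparisons as descriptive.
- Label the 6-week QoR-15 and STAI-6 data as secondary or descriptive.
- In section 4.4, say that the power holds only if the chosen NRS summary follows Table 1, with 50 analysed per group. On that condition it is about 93% under (b) and about 81% under (a) with Bonferroni, and at least that with Holm.
- If the summary is a three-day mean, state how many days the effect is assumed to last and give the power for that case.

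The cost is protocol wording, with no extra patients or data. The downside is a lower stated power under (a), with little margin above 80% if patients are lost, or the loss of primary status for three outcomes under (b).
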